9.7.7. Inferential analyses of the secondary outcomes

The analysis of SVT will be similar to the SCRI design analyses for gout. The analysis of ION will be similar to the cohort design analysis for PMR and GCA.

Sensitivity analysis of alternative definition of ION

• The number of cases and the incidence rate (or cumulative incidence) among vaccinated and preventative care comparators who are identified using the sensitivity analysis HOI definition of ION (Table 3 Column 10) will be reported.Further analyses consistent with the primary (1°) analysis for the cohort design (i.e.analysis of separate doses) will be conducted if an appropriate number of cases are identified to allow meaningful inference.

9.7.8. Sensitivity analysis to evaluate the impact of the COVID-19 pandemic

Sensitivity analyses will exclude exposures from the analytical cohort for which followup ended after February 1, 2020. These sensitivity analyses will be conducted for each HOI and will be aligned with the primary (1°) SCRI and cohort analysis as described in Table 1 and sections 9.7.6 and 9.7.7. These sensitivity analyses will allow for an evaluation of the robustness of the primary findings after excluding cases and vaccinations during the COVID-19 pandemic. The sensitivity analyses will be descriptive if the exclusion of *participants* after February 1, 2020 compromises the sample size such that there is insufficient power to generate meaningful estimates. Such descriptive analysis will report the number of cases in the risk and control windows (for the SCRI design) or the incidence rate (or cumulative incidence) for the cohort design.

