Censoring events. Exposed person-time will be defined as the period between the index date and the earliest of the following events:

- End of study period (defined as the lesser of 183 days after the index date or Dec 31. 2021)
- Date of disenrollment from Medicare Parts A, B, and D
- Date of death
- Date of *Shingrix* vaccination among comparators
- Date of *Zostavax* vaccination
- Date of first diagnosis of the outcome of interest.

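### For PMR, GCA and ION, the COVID-19 sensitivity rule in 9.7.8, read with the 9.7.6 censoring list, selects late index dates on the outcome; the cut should use the scheduled end of follow-up

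*Combined protocol and SAP*

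**What the plan says.** Section 9.7.8 sets the rule: the sensitivity analyses will "exclude exposures from the analytical cohort for which followup ended after February 1, 2020". Its aim is to see whether the findings hold "after excluding cases and vaccinations during the COVID-19 pandemic". Its scope is wide: "These sensitivity analyses will be conducted for each HOI and will be aligned with the primary (1°) SCRI and cohort analysis", with reference to 9.7.6 and 9.7.7. If too little power remains, the analysis becomes descriptive and reports, for the cohort design, the incidence rate or cumulative incidence. Annex 5 records that CBER asked for this check.

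Section 9.7.6 is the only place that says when an individual's cohort time stops: "Exposed person-time will be defined as the period between the index date and the earliest of the following events". The list contains:
- "End of study period (defined as the lesser of 183 days after the index date or Dec 31. 2021")
- disenrollment, death and Zostavax vaccination
- "Date of first diagnosis of the outcome of interest"
- one item that exists in one arm only, Shingrix "vaccination among comparators"

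For the SCRI outcomes, 9.7.6 instead requires enrollment through the end of the control interval, which fixes the follow-up.

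**The concern.** A calendar restriction should depend on the index date or on calendar time, not on what happened to the person. If follow-up ends as in the 9.7.6 list, whether a late index date survives the cut depends on whether the person had an event. A vaccinee indexed in November 2019 who develops PMR in January 2020 is kept. A vaccinee indexed on the same day who remains well and enrolled is removed with all person-time. Comparators have one more way to be kept, a later Shingrix dose, and the supplemental analysis in 9.7.9 expects such crossover.

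At stake is the value of a regulator-requested robustness check. A rate or hazard ratio that shifts because of the selection rule could be taken for a pandemic effect.

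**Working it through.** **Dates.** 2 August 2019 + 183 days = 1 February 2020. Index dates from 1 January 2018 to 2 August 2019 (579 days) always complete follow-up by the cut-off. Those from 3 August 2019 to 1 February 2020 (183 days) do not, unless an early-ending event occurs.

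**Base rate.** Section 9.7.8 gives no figure, so the PMR rate comes from Table 5. To check its scale, use the Poisson-regression formula N = [1.960·√V0 + 0.8416·√V1]² / (μ·rate·ln(RR)²), with exposed share 0.2, RR 2 and μ = 0.5 year:
- V0 = 1/(0.2 × 0.8) = 6.25
- V1 = 1/0.8 + 1/(0.2 × 2) = 3.75
- N = (4.900 + 1.630)² / (0.5 × 0.000405 × 0.4805) = 438 239

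This is the plan's figure, so 0.000405 acts as a rate per year, or 40.5 per 100 000 person-years (PY).

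**Incidence under the realised-end rule.** Assume uniform accrual. Late index dates have 0 to 182 days before the cut-off, mean 91. They contribute 183 × 91/183 = 91 full-follow-up day-equivalents of events, but almost no person-time.
- Share of retained events from late index dates: 91/(579 + 91) = 13.6%.
- Rate inflation: (579 + 91)/579 = 1.157, so 40.5 becomes about 46.9. Counting the little person-time retained gives 46.8 per 100 000 PY in each arm (+16%).

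**Hazard ratio when the true value is 1.** Assumptions not in the documents: constant hazards, death plus disenrollment at 5-10% per year in both arms, comparator Shingrix uptake at 2-15% per year, and a 1:4 ratio at every index date. Let h be the outcome hazard and c the other ending hazards. For a late index date K days before the cut-off:
- events on day t are proportional to h·exp(−(h+c)t), for t < K
- the retained risk set on day t is proportional to exp(−(h+c)t) − exp(−(h+c)K)

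For early dates the second term is absent. The log HR b solves Σ[events_v − D·R_v·e^b/(R_c + R_v·e^b)] = 0 over days and strata. Here D is all events, and R_v and R_c are the vaccinee and comparator risk sets.

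At 5% death/disenrollment and 5% uptake, 1.25% of late vaccinees and 2.46% of late comparators are kept. Their rates are 4 805 and 2 422 per 100 000 PY, and the late-stratum HR is 1.98.

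| Analysis, true HR 1 | HR obtained |
|---|---|
| No calendar adjustment, same index-date distribution | about 1.00 |
| Stratified by index month, uptake 2-15%, death/disenrollment 5-10% | 1.02-1.11 |
| Any stratification, comparator uptake zero, same index-date distribution | 1.00 |
| No calendar adjustment, vaccinee late accrual 1.5 times higher | about 1.07 |
| Everyone censored on 1 February 2020 | 1.00 |

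The fourth row can be checked by hand: (579 + 1.5 × 91)/(579 + 91) = 1.07. The month-stratified shift arises because late comparators kept through Shingrix enlarge the comparator risk sets. Without stratification, the early risk sets swamp them.

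**SCRI outcomes.** If follow-up ends at the scheduled end of the control window, there is no selection. If the event date were used instead, over 762 uniform index days, an event on day k is kept for 762 − k of them. With the mean k of each window:
- GBS: (762 − 21.5)/(762 − 63.5) = 1.06
- gout: (762 − 15.5)/(762 − 45.5) = 1.04

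**The case against.** The strongest reply is that follow-up in this protocol means the fixed window. Section 9.1 speaks of a 183-day follow-up period, and 9.7.6 says everyone is followed for 183 days from Dose 1. Section 9.3.2 requires both qualifying claims to fall within the designated follow-up interval, which could not happen for outpatient cases if follow-up stopped at the diagnosis date. The 9.7.6 list defines person-time and does not use the term follow-up for it. On this reading, 9.7.8 already amounts to an index-date cut-off.

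That reading has real support and would be harmless. It does not settle the matter. Sections 9.7.2 and 9.7.9 also use follow-up for the time a person actually contributes, and 9.7.8 neither says scheduled nor gives an index-date limit. A programmer could apply it either way.

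Three stronger inferences are tempting, and the documents do not support them:
- *The arms are inflated unequally.* Overall incidence rises by about 16% in both. Only the late-index stratum differs sharply.
- *The hazard ratio is necessarily biased.* The shift depends on uptake, attrition and accrual figures that the documents do not give, and on how calendar time is modelled. Section 9.9 says calendar month-year will be a covariate, but does not specify stratification. Section 9.7.10 ties adjustment to a standardised difference above 0.10. In the 5%/5% case, late dates make up about 0.4% of vaccinees and 0.8% of comparators (183 × 1.25% = 2.3 against 579 early days; 183 × 2.46% = 4.5 against 579), a standardised difference of about 0.05.
- *The SCRI outcomes share the fault.* Section 9.7.6 fixes their follow-up, and they have no arms.

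**Conclusion.** The point stands for PMR, GCA and ION as a defect of wording with a material consequence under one plausible reading. On that reading the rule selects on the outcome. The firmest result is the 16% inflation of incidence in both arms. It rests on uniform accrual from January 2018 and hardly at all on the assumed attrition and uptake. It falls directly on the rate or cumulative incidence that the plan would report if power is short.

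The effect on the hazard ratio is modest and conditional: none to about 1.11 with a common index-date distribution over the assumed ranges, and about 1.07 without calendar adjustment if vaccinees accrue 1.5 times faster in the last six months. A reader might infer that the primary results are compromised. They are not, because the rule applies only to this sensitivity analysis.

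**What to change.** In 9.7.8, define the exclusion by the scheduled, not the realised, end of follow-up. For PMR, GCA and ION, include only index dates with index + 183 days on or before 1 February 2020, that is, index dates up to 2 August 2019. This costs one sentence. It gives up the roughly 13.6% of events that the realised-end rule would keep from late index dates.

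Alternatively, keep all index dates before 1 February 2020 and censor everyone administratively on that date. This keeps those events and restores the deleted event-free person-time. It needs a second sentence on how to treat a PMR or GCA case whose first outpatient claim falls before the cut-off and whose second falls after it, since 9.3.2 requires both within the follow-up interval.

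For GBS, gout and SVT, only confirm that the date compared with 1 February 2020 is the scheduled end of the control window, not the event date.

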9.7.9. Statistical models

Statistical models for the SCRI design

The primary, secondary and sensitivity analyses of the SCRI design will use a conditional Poisson regression model. This will estimate the incidence rates generated in risk and control windows of the same individual accounting for the within *participant* dependence using generalized estimating equations for robust variance estimation. The conditional Poisson regression model is a multinomial model, where time-fixed confounders within each stratum are controlled by conditioning on the sum of events in this stratum³¹. The general form of a conditional Poisson regression model can be written as:

n_{ik}~Poisson(λ_{ik}e_{ik})

$$\log(\lambda_{ijk}) = \phi_i + \theta_k$$

The response variable is n_{ik} , the number of events for the *i*th individual in the k (risk or control) interval. The log of the time spent in the interval (lne_{ik}) is the offset term.

In the model, λ_{ik} denotes the incidence within each interval, ϕ_i is the effect for individual i (log of baseline incidence of HOI for individual i), and β_k is the effect for risk group k³². The model generates incidence rate ratio with a 95% CI.

PROC GENMOD with the Poisson distribution, a log link function, and the EXACT statement will be employed using SAS 9.4 to perform a conditional Poisson regression model. The main model will include the dependent variable (Y) as the number of events, a binary independent variable as the interval (risk or control), and the log of person days in the interval as the offset term.

The Deviance goodness of fit test will be used to evaluate the Poisson model fit. When using PROC GENMOD to fit a Poisson regression model, the "Criteria For Assessing Goodness Of Fit" output provides the Value/DF ratio. The ratio should be close to 1 to denote a good fit of the model to the data. If the Value/DF ratio is ≥ 2 , there is overdispersion, which can result in underestimation of standard error and thus overestimate statistical significance. The "DSCALE" or "PSCALE" options in the GENMOD procedure use "deviance chi-square" and "Pearson chi-square" to make the adjustment for over-dispersion. A negative binomial link function will be used should there be overdispersion.

Temporal scan statistics

Temporal scan statistics will be used as a supplemental method for assessing the possibility of an association between RZV vaccination and an HOI during the respective follow-up period. This method evaluates whether there is any statistically significant temporal clustering of cases, the existence of which may suggest, although not confirm, an association.

Statistical models for the cohort design

Separate analysis for Dose 1 and Dose 2. The primary analysis for the cohort design will be conducted using a Cox proportional hazards regression model. This is a semiparametric model in that it assumes a parametric form for the effects of the explanatory variables and an unspecified form for the underlying survival function. The general form of a Cox proportional hazards regression model can be written as:

 $h_i(t,x) = \lambda_0(t) \exp[\beta_1 x_{i1} + \dots \beta_k x_{ik}]$

where, h(t) is the expected hazard at time t; $\lambda_0(t)$ is the baseline hazard function and represents the hazard when all predictors are equal to 0.

PROC PHREG will be employed using SAS 9.4 to estimate the Cox proportional hazards regression model. The effect estimate generated from Cox proportional hazards model is hazard ratio, expressed as:

$$HR(t,1,0,\beta) = \frac{h(t \mid x = 1,\beta)}{h(t \mid x = 0,\beta)} = \exp(\beta)$$

where x (1,0) denotes to exposure status, and β is the estimated parameter from the regression model. Violations of the proportional hazard assumption will be evaluated

CONFIDENTIAL

using a graphical approach by plotting the log[-logS(t)] versus log(t) and the Schoenfeld residuals by time, by testing the interaction between the covariates and log(t), and by using the assess statement available in the PROC PHREG procedure. Non-parallel lines or none-zero slope in the graphical approach, a significant interaction term, and a significant supremum test would indicate a violation of the proportional hazards assumption. If the proportional hazard assumption is violated, an interaction term of time and the variable of interest will be included in the model.

Combined analysis of Dose 1 and Dose 2 yielding one risk estimate. A partly

conditional survival model will be used in the secondary analysis of combined doses. Since an individual may contribute more than one observation in the analysis (i.e., Dose 1 and Dose 2), this model is appropriate as it estimates the effect of longitudinal measures, in this case dose, on survival allowing for repeated measures for each individual^{33,34}.

Whereas typically survival is modeled as the time from study entry to the event, i.e., event time, D_i , in partly conditional survival analysis, regression parameters depend upon the time of measurement, S_i , for the predictor (i.e., dose receipt) and the time of measurement for the event to measure the follow up time since the measurement, D_i-S_i . This is considered partly conditional since the hazard function that is being modeled conditions on the covariate history through S_i . As a result, there are multiple event times for each individual which corresponds with the repeated measures for each dose.

A general form of the regression model for the hazard is shown below,

$$\lambda_{ik}(t*|\mathbf{Z}_{ik}, 0 \leq s_{ik} \leq T_i) = g[\lambda_0(t*, s), \boldsymbol{\theta}(t*, s)^\top \mathbf{Z}_{ik}]$$

where T_i is the time to event (or censor) for *participant i*, s_{ik} denotes measurement times for each dose, $t^* = t - s_{ik}$ measures the follow-up time since dose, $g(\lambda, \eta)$ is a link function, $\lambda_0(t^*, s)$, is the baseline hazard, $\beta(t^*, s)$ is the regression coefficient, and Z_{ik} is a vector of covariates associated with *participant i*, at time s_{ik} .

The analysis will be conducted using SAS 9.4, and standard errors will be calculated using a robust sandwich estimator for repeated measures survival data.

Combined analysis of Dose 1 and Dose 2 yielding separate risk estimates. To generate a separate risk estimate for each dose in a combined analysis, where a binary indicator defines the Dose 1 and Dose 2 risk windows, a time-varying Cox proportional hazards regression models will be used. In the time-dependent model, we allow the risk window to vary for each dose. The time after dose 1 until dose 2 or end of follow-up if no dose 2 occurs defines the dose 1 risk window, and the time from dose 2 until end of follow-up defines the dose 2 risk window. Thus, a *participant* who receives two doses will contribute time to the dose 1 risk window and the dose 2 risk window. In the unvaccinated comparators the time from index date to end of follow-up is considered unexposed time. A general form of time-dependent Cox models can be written as:

 $h_i(t,x) = \lambda_0(t) \exp[\beta_1 x_{i1} + \dots \beta_2 x_{i2}(t)]$

where x_{i1} represents a time-independent variable, and x_{i2} represents the time-dependent variable. This analysis will use the full cohort and obtain estimates for both doses

whereas the primary separate dose analysis either ignores dose 2 or includes only the subset of the sample who received 2 doses.

This analysis allows us to use the full cohort to compare the findings to the primary separate dose analysis. The primary Dose 1 analysis ignores Dose 2, and as such the events after Dose 2 may be attributed to Dose 1, thereby increasing the HR for Dose 1 (and its unknown which dose carries the highest risk). The primary Dose 2 analysis only includes individuals who did not experience the event after Dose 1, which could reflect potentially the more robust individuals. This could bias the estimate towards the null, and it is difficult to determine whether the estimate is a function of the vaccine or the characteristics of the Dose 2 subgroup. The time-varying model for this analysis uses the entire cohort, and attributes events to the respective dose risk window yielding a HR for each dose. Therefore, the full cohort sensitivity analysis allows us to estimate the hazard for each individual dose risk and to compare the results with the primary analysis estimates.

The effect estimates generated from the time-dependent Cox proportional hazards model will be a hazard ratio for Dose 1 relative to unexposed and a hazard ratio for Dose 2 relative to unexposed. Both hazards are generated in the same model with the full cohort, using time since the Dose 1 index date or the preventive care visit.

Sensitivity analysis for receipt of the Dose 1 and Dose 2 on schedule. The sensitivity analysis will be restricted to the sub-sample of individuals who receive both RZV doses on schedule per US label. This will test the sensitivity of the primary and secondary analyses, which examine the HOI incidence regardless of the dose spacing. This will follow the primary separate dose analysis and the secondary combined dose analysis.

Supplemental analysis

Some individuals in the analysis may contribute person-time both to the comparison group and (subsequently) to the RZV-vaccinated group. At CBER's request, a supplemental analysis will be conducted for the primary analysis, excluding from the control arm those *participants* who received RZV at any point, so that each *participant* contributes person-time to only one arm.

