 - A self-controlled risk interval design will be used to assess the risks of GBS, gout, and SVT (a secondary outcome).
 - A cohort design with concurrent controls will be used to assess the risks of PMR, GCA and ION (a secondary outcome).
- **Population:**The study population is a nationally representative sample of
US Medicare beneficiaries aged 65 years and older, who are
enrolled in Medicare Parts A, B, and D.

Variables: The exposure is receipt of at least one dose of RZV. The dependent variable is the occurrence of the health outcome of interest. Several covariates include age, sex, region of residence within US, calendar year-month, concomitant vaccination with other preventive immunizations, certain comorbidities, healthcare visits.

- **Data sources:** The study will use the CMS Chronic Conditions Warehouse Medicare database that includes inpatient, outpatient, physician, and prescription claims for all health services and medications provided for Medicare enrollees with Parts A, B, and D. Data from January 2017 through December 2021 will be used in this study.
- Study size:Sample size calculations suggest that the study will ultimately
have at least 80% power to reject the null hypothesis of no
association if the true relative risk is ≥ 4 for GBS, ≥ 2 for
gout, ≥ 2 for PMR, and ≥ 3 for GCA.

The estimated number of individuals for each primary outcome (assuming all individuals receive 2 doses) is:

• GBS: 1 000 000 to detect a relative risk of 4.0 or more;

- Gout: 70 000 to detect a relative risk of 2.0 or more;
- PMR: 438 239 to detect a relative risk of 2.0 or more;
- GCA: 723 362 to detect a relative risk of 3.0 or more.
- Data analysis:The analysis plan will include descriptive measures to
characterize exposed and unexposed individuals, conditional
Poisson regression models for the SCRI, and Cox proportional
hazards regression models for the cohort design outcomes.
- Milestones:The milestones are 11 September 2020 (Actual date) for start
of data collection, Q4, 2024 (Tentative) for end of data
collection and final report submitted to the Center for
Biologics Evaluation and Research (CBER) and the European
Medicines Agency (EMA) 30 June 2027.

Note: the above timelines are tentative and subject to change.

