9.1. Study design

This study is a Targeted Safety Study (TSS) and a Post-Authorization Safety Study (PASS) that will assess the risk of new-onset GBS, gout, and SVT following RZV exposure using a SCRI design; and the risk of new-onset PMR, GCA, and ION following RZV exposure using a cohort design with a concurrent comparator.

The study population will comprise approximately 4 to 5 million CMS Medicare beneficiaries age 65 years and older who received at least one dose of RZV.

RZV exposure will be defined as receipt of at least one dose of vaccine; sensitivity analyses will be conducted to assess the risk of outcomes when Dose 2 is received per US dosing schedule, i.e. 2-6 months after Dose 1.

This study will be conducted using CMS CCW Medicare claims data (described in Section 9.4.1).

Table 1 provides an overview of the study designs for the primary health outcomes ofinterest (HOI).

Primary objectives 1 & 2: SCRI

To assess the risk of new-onset GBS and gout, a SCRI design will be used¹⁰. This design is a special (and simpler) case of both the case-crossover^{11,12} and the self-controlled case series^{12,13} designs, in which the cumulative number of cases in pre-specified risk and control intervals (or "window") are compared. Individuals serve as their own control. The analysis is conditioned on the interval (or "window"), and only RZV vaccinees who experience the HOI in the risk or the control interval contribute to the analysis. The SCRI design is ideal for acute outcomes and transient exposures¹³. The advantage of the SCRI design is the implicit control for time-fixed potential confounders such as sex, race/ethnicity and stable chronic medical conditions. However, potential time-varying confounders, such as age, seasonality, and possibly medication use, may introduce bias unless they are explicitly controlled for with in the analysis.

Primary objectives 3 & 4: Cohort design

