9.3.3. Covariates

Covariates to be evaluated include the following, some of which will be used to adjust or stratify the cohort during the analytic modeling:

- Region of residence within US [as defined by either Department of Health and Human Services (11 regions) or Census Bureau (4 regions)]
- Calendar year-month of vaccination or preventive care visit
- Age in years at vaccination or preventive care visit (aggregated into age groups: 65-69, 70-74, 75-79, 80-84, 85+)
- Sex (binary as male/female)
- Race and ethnicity (e.g., white, black, Asian, Hispanic, North American Native, other)
- Concomitant vaccination (e.g., influenza, pneumococcal, etc.)
- Certain immunocompromising conditions (e.g., transplant, cancer, autoimmune/inflammatory condition, etc.)
- Certain other co-morbidities (e.g., diabetes mellitus, chronic obstructive pulmonary disease, congestive heart failure, etc.)

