9.3.4. Potential confounding variables and effect modifiers

A confounder is defined as any variable that is associated with both the exposure and the study HOI. Since a confounder cannot be on the causal pathway from exposure to the outcome, all confounders will be captured in the 365 days preceding the index date, i.e., RZV Dose 1 and Dose 2 vaccination date and the RZV unvaccinated comparator preventive care visit for the cohort design. All confounders identified using Medicare enrollment and medical or prescription claims data will be used for covariate adjustment in multivariable models. Propensity score methods will be considered for confounding adjustment, depending on identified imbalances in the observed covariates between the exposed and comparator groups. Confounding variables defined by health care services and comorbidities will be identified using a combination of ICD-10, CPT and HCPCS codes.

- **Demographic variables** will include age, sex, and race and ethnicity (i.e., white, black, Asian, Hispanic, North American Native, and other/unknown based on the US government categories)
- **Healthcare service variables** will include admissions to skilled nursing facilities (SNFs), number of hospitalizations, number of ED visits and Durable Medical Equipment (DME) use. These will be considered to control for potential imbalances between RZV vaccinees and RZV unvaccinated comparators in health impairment requiring more intensive services. The place of service and revenue code on the claim are used to designate the type of service setting.
- **Preventive care services** will include receipt of age-recommended vaccine (e.g., influenza, pneumococcal, and tetanus, diphtheria, pertussis). These will be

considered to control for potential healthy adherer bias that could result in imbalances in healthcare services and prior health seeking behavior patterns between RZV vaccinees and RZV unvaccinated comparators. Table 2 lists the preventive care services. Since mammography, bone mineral density, and colorectal screening are criteria for the unvaccinated comparator selection, these are not included as confounders in the analysis.

- **Medical comorbidities specific to PMR/GCA**. Potential risk factors specific to these conditions may include:
 - Age, which is found to be the strongest risk factor;¹⁹
 - Female sex is found to be a risk factor;¹⁹
 - Race/ethnicity as a significantly lower incidence is reported in African, Asian, Latinos;¹⁹

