9.9. Limitations of the research methods

The section describes the potential limitations that impact the inferences that can be drawn from this study along with the likely success of efforts taken to reduce bias.

Study design. Despite the careful selection of appropriate study designs to address the study objectives, there are some limitations. The SCRI design mitigates bias through implicit control for time-fixed confounders. A limitation is that it does not control for time-varying confounders. With the short risk windows for this study, there may be minimal change in confounders, and thus minimal bias would be introduced.

A limitation of the cohort analysis is dis-enrollment from Medicare Parts A, B, and D, which could impact the 365-day baseline period. The feasibility assessment showed that requiring more than 365 days would reduce the sample size because individuals lose Parts A, B, or D coverages. Further, individuals who receive RZV close to age 65, the age at which individuals qualify for Medicare, may not have a full year of enrollment prior to the vaccination date. Consultation with clinical experts confirmed that the 365-day baseline would be adequate to exclude prevalent cases of the HOIs. According to the sample size estimates, the large sample size in the CMS Medicare population should be sufficient, even if the sample is reduced due to less than 365 days of enrollment in Parts A, B, and D prior to the vaccination or preventive care visit date.

Data sources: limitations of the CCW Medicare data.

Services covered by Medicare Advantage (Part C) plans are not included in the CCW Medicare data. Older adults who opt to purchase supplemental insurance are covered under the Medicare Advantage plans, or Part C. All medical encounters and services are paid for by the supplemental insurance, and thus data on these individuals are missing.

Data on clinical metrics, such as laboratory values and illness severity, that could have been used for case identification are not available in the claims data.

Analytic methods. The analytic models selected for the analyses have minimal assumptions, and most of which can be verified through analytic tests and graphical display of the data. However, they could still have some unverifiable assumptions.

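### No SCRI analysis uses the listed concomitant-vaccination covariate; a sensitivity analysis excluding co-vaccinated RZV doses would be a cheap improvement

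*Combined protocol and SAP*

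**What the plan says.** The Abstract names "concomitant vaccination with other preventive immunizations" among the study covariates. Section 9.3.3 lists "Concomitant vaccination (e.g., influenza, pneumococcal, etc".) among covariates to be evaluated, "some of which will be used to adjust or stratify the cohort during the analytic modeling".

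Section 9.7.9 gives the SCRI main model as an event count with "a binary independent variable as the interval (risk or control), and the log of person days in the interval as the offset term". It says that "time-fixed confounders within each stratum are controlled by conditioning on the sum of events in this stratum".

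Section 9.1 warns that time-varying confounders, with age, seasonality and possibly medication use as its examples, "may introduce bias unless they are explicitly controlled for with in the analysis". Section 9.9 concedes that the SCRI does not control such confounders and adds: "With the short risk windows for this study, there may be minimal change in confounders, and thus minimal bias would be introduced".

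Section 9.7.6 plans one SCRI adjustment, for seasonality, in secondary analyses of GBS and gout. Section 9.7.7 analyses SVT in the same way as gout.

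**The concern.** A vaccine given on the same day as RZV starts its own post-vaccination period on the same day. For GBS that period is days 1–42, and for gout and SVT days 1–30. If its effect lasts about as long as the risk window, it has passed by the time the control window opens. The other vaccine is therefore a time-varying exposure aligned with the risk window, and conditioning on the person cannot remove it.

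The argument in section 9.9 about short windows covers slow drift in age or comorbidity. It does not cover an exposure that begins on the vaccination date. The seasonality adjustment works on calendar time, not on each person's vaccine dates. The temporal scan statistics would show the same cluster whichever of two same-day vaccines caused it.

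What is at stake is attribution. The study asks whether RZV raises these risks, and as written no output separates RZV alone from RZV with another vaccine.

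**Working it through.** **Is the variable used anywhere in the SCRI?**

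- Section 9.7.6, SCRI inclusion: RZV receipt, first occurrence in 365 days and enrollment. Other vaccines are not mentioned.
- Section 9.7.6, windows, secondary and sensitivity analyses: control-window length, separate doses, on-schedule doses and seasonality. Other vaccines are not mentioned.
- Sections 9.7.7 (SVT) and 9.7.8 (COVID-19): nothing.
- Section 9.3.4: "all confounders will be captured in the 365 days preceding the index date". This is written for the cohort design and does not reach same-day or later vaccines.
- Section 9.7.10: adjusts for variables whose standardized mean difference between RZV recipients and unvaccinated comparators exceeds 0.10. The SCRI has no such contrast.
- The only censoring at another vaccine product is for Zostavax, in the cohort design (section 9.7.6).

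**The plan's own event counts (Table 4).** The method for self-controlled case series gives n = (1.96 + 0.8416√B)²/A. Here A = 2[(ρw/q) ln ρ − ln q], B = (ln ρ)²/A × ρw(1 − w)/q², q = ρw + 1 − w, ρ is the relative risk and w is the share of observed time in the risk window.

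- Gout, ρ = 2, w = 0.5: A = 0.1133, B = 0.9426, n = 68.09 (stated 68).
- GBS, ρ = 4: n = 19.07 at w = 0.5 and 20.23 at w = 42/78 (stated 20).

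The plan's counts are reproduced. No stated figure is in dispute.

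**Size of the bias, same-day vaccine, true RZV IRR of 1.** Both inputs are assumptions, because the documents give neither.

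Expected IRR = (1 − c) × 1 + c × r = 1 + c(r − 1)

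| c | r = 1.5 | r = 2 |
|---|---|---|
| 10% | 1.05 | 1.10 |
| 20% | 1.10 | 1.20 |
| 30% | 1.15 | 1.30 |

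**Direction by timing.** Take GBS with full 42-day windows, c = 20%, r = 2 and a 42-day effect of the other vaccine, given k days after RZV:

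IRR = [1 + 0.2(42 − k)/42] / [1 + 0.2k/42]

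| k (days) | 0 | 7 | 14 | 21 | 28 | 42 |
|---|---|---|---|---|---|---|
| IRR | 1.20 | 1.13 | 1.06 | 1.00 | 0.94 | 0.83 |

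**Chance of a false harmful signal.** This uses an exact conditional binomial test with the upper tail at 0.025 and a true RZV IRR of 1.

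- GBS, 20 events, w = 42/78, critical value 16 in the risk window: 1.5% unbiased, 1.9% at IRR 1.05, 3.7% at 1.20, 5.3% at 1.30.
- Gout, 68 events, w = 0.5, critical value 43: 1.9% unbiased, 9.3% at IRR 1.20.
- Gout at the expected study size: section 9.2.2 expects a little more than 2 million eligible vaccinees, or about 4 million doses if all receive two. At 200 per 100 000 person-years and 30-day windows this is 4 000 000 × 0.002 × 30/365.25 × 2 = about 1,314 events. With that total held fixed, the chance is 2.2% unbiased, 13% at IRR 1.05, 39% at 1.10 and 90% at 1.20.

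Table 4's per-window gout entry (8.706 per 100 000) does not match its own rate of 200, which gives 16.43. Using 8.706, the total would be about 40 × 8.706 × 2 = 696 events. That is still far more than 68.

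**The case against.** The strongest reply is that this is a conditional gap and not a demonstrated bias. The documents give no co-administration share and no reason to think that another vaccine raises gout or SVT risk. Section 9.9 already discloses that time-varying confounders are not controlled. Section 9.3.3 leaves room to use the listed covariates, and section 9.7.9 describes only the main model. All of this stands, and it limits the point to a missing specification.

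A reader might infer that a few co-vaccinated cases among about 20 could decide the GBS result. The figures do not support that: across the assumed range the false-signal chance goes from 1.5% to at most 5.3%.

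A reader might also infer that any nearby vaccine inflates the IRR. That holds only on or close to the RZV date. From about three weeks after RZV the bias turns downward.

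A table of co-vaccinated cases has limits too. Section 10 suppresses cells below 11. With 20 GBS cases and 10–30% co-vaccinated, 2 to 6 cases would be split over two windows, and every such cell would be suppressed.

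What the reply does not answer is that the plan names the variable, warns about this class of confounder, and then gives the SCRI no way to examine it.

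**Conclusion.** The gap is real and modest, and closing it is a cheap improvement. Concomitant vaccination is a listed covariate that no SCRI analysis uses, and the within-person design does not remove the effect of a same-day vaccine that raises the outcome risk. On assumed shares of 10–30% and relative risks of 1.5–2, the IRR with no RZV effect would be 1.05–1.30. On the same assumptions GBS is little affected at 20 events. Gout, with many more events, would be sensitive to a bias of this size if another vaccine raised gout risk, and nothing in the documents says that one does. The stronger conclusion, that the planned SCRI estimates are biased or that a GBS finding could not be interpreted, is not supported.

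**What to change.** Add to sections 9.7.6 and 9.7.9, for GBS, gout and SVT, a sensitivity analysis that repeats the primary SCRI analysis after excluding RZV doses with any other vaccine claim (Part B or Part D) on the RZV date or within one risk-window length before it.

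Define the exclusion from the RZV date and never from the outcome date, so that a dose's risk and control person-time leave together. An exclusion timed back from the outcome would itself bias the result. With a harmless vaccine given 7 days before RZV, it would remove GBS cases on days 1–35 and no control-window cases. The null IRR would be 1 − c × 35/42, which is 0.92 at c = 10% and 0.83 at c = 20%.

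Report co-vaccinated cases by risk and control window where the section 10 suppression rule allows. Section 9.7.4 already plans such a report for infection before GBS. State in section 9.9 that an IRR that changes materially in this analysis cannot be attributed to RZV alone, and that vaccines given after RZV are not removed and can bias in either direction.

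The cost is one extra model run per SCRI outcome on claims already acquired, a code list for other vaccines (section 9.3.1 gives RZV codes only), and a wider interval from fewer cases. Sample size is not an obstacle. Even if 30% of doses were excluded, the plan's requirements would become 1 000 000/0.7 = about 1.43 million vaccinees for GBS and 70 000/0.7 = 100 000 for gout, against about 2 million expected.
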